#### Safety Endpoints

At  $75 \pm 5$  days following each transplant and  $365 \pm 14$  days following the first and final islet transplant:

• The incidence and severity of AEs related to the islet transplant procedure including: bleeding (>2 g/dL decrease in hemoglobin concentration); segmental

- portal vein thrombosis; biliary puncture; wound complication (infection or subsequent hernia); and increased transaminase levels (>5 times upper limit normal [ULN])
- The incidence and severity of AEs related to the immunosuppression including: allergy; reduction in GFR; increase in urinary albumin excretion; addition or intensification of anti-hypertensive therapy; addition or intensification of anti-hyperlipidemic therapy; oral ulcers; lower extremity edema; gastrointestinal toxicity; neutropenia, anemia, or thrombocytopenia; viral, bacterial, or fungal infections; and benign or malignant neoplasms
- The incidence of a change in the immunosuppression drug regimen
- The incidence of immune sensitization defined by presence of anti-HLA antibodies absent prior to transplantation

At  $75 \pm 5$  and  $365 \pm 14$  days following the first islet transplant:

• The incidence of worsening retinopathy as assessed by change in retinal photography

## 3.1.2 Additional Hypothesis Generating Endpoints:

At  $75\pm 5$  days following the second and third transplants, the following will be reported for the subset who receive a second transplant who also have data collected and also for the subset who receive a third transplant.

- the proportion of insulin-independent subjects
- the percent reduction in insulin requirements
- HbA1c
- MAGE
- LI
- HYPO score
- Basal (fasting) and 90-min glucose and c-peptide (MMTT)
- β-score
- C-peptide: (glucose X creatinine) ratio
- Acute insulin response to glucose (AIRglu), insulin sensitivity, and disposition index derived from the insulin-modified frequently-sampled intravenous glucose tolerance (FSIGT) test
- Glucose variability and hypoglycemia duration derived from the continuous glucose monitoring system® (CGMS)
- QOL

At  $365 \pm 14$  days following the last islet transplant will include the change in the following measures from the results obtained at  $75 \pm 5$  days following the last islet infusion:

- the proportion of insulin-independent subjects
- the percent reduction in insulin requirements
- HbA1c
- MAGE
- LI
- Clarke score
- HYPO score
- Basal (fasting) and 90-min glucose and c-peptide (MMTT)
- β-score
- C-peptide: (glucose X creatinine) ratio
- Glucose variability and hypoglycemia duration derived from the continuous glucose monitoring system® (CGMS)
- QOL

#### 3.1.3 Additional Exploratory Endpoints

Section 9 describes the mechanistic assays that will be done. Additional exploratory analyses will generate metabolic and mechanistic hypotheses for further investigation. Each of the following tests allows for the quantification of several metabolic parameters explained in Section 9. End points from subjects in CIT-07 will be compared to subjects from University of Pennsylvania in CIT-05 in Section 10.

- A Glucose-potentiated arginine (GPA) test  $^{11}$  will be conducted at  $75 \pm 15$  days after each transplant and at  $365 \pm 14$  days after the last transplant and the endpoints of acute c-peptide and insulin responses to arginine computed and analyzed.
- Among subjects who are insulin independent, the glucose potentiation slope and  $\beta$ -cell secretory capacity will also be calculated and analyzed at  $75 \pm 15$  and  $365 \pm 14$  days after last transplant.
- Glucose counter-regulation (paired eu- and hypoglycemic clamp studies) $^{68, 69, 154, 155}$  will be conducted pre-transplant and at  $180 \pm 30$  days and  $365 \pm 60$  days after the last transplant.
- Immunophenotyping of lymphocyte subsets will be performed at baseline, days 7 and 28, and months 2.5, 6, 9 and 12.
- HiD (high-resolution multiparameter (flow cytometry) of B lymphocyte subsets will be performed at baseline and on days 7 and 28, and months 5 and 6. These time points were chosen because they are likely to be most informative for analyzing B cell depletion and reconstitution following treatment with anti-CD20.
- B lymphocyte repertoire analysis (CDR3 spectratyping) will be performed on CD19+ cells at baseline, and months 6, 9, and 12. Samples will be collected for clone

tracking analysis at baseline and at all subsequent study time points.

• ELISpot analysis of islet-reactive peripheral blood T Lymphocytes will be performed at baseline, days 0, 7, and 28, and months 2.5, 6, 9, and 12. If the ELISpot is positive, the specificity and cytokine profile of reacting T cells will be characterized in father detail.

• The memory B cell response to influenza will be analyzed at baseline and at month 6.

#### 4. SELECTION OF SUBJECTS

#### 4.1 Inclusion Criteria

Patients who meet *all* of the following criteria are eligible for participation in the study:

- 1. Male and female patients age 18 to 65 years of age.
- 2. Ability to provide written informed consent.
- 3. Mentally stable and able to comply with the procedures of the study protocol.
- 4. Clinical history compatible with T1D with onset of disease at <40 years of age and insulin-dependence for ≥5 years at the time of enrollment, and a sum of patient age and insulin dependent diabetes duration of ≥28 years.
- 5. Absent stimulated c-peptide (<0.3ng/mL) in response to a mixed meal tolerance test (MMTT; Boost® 6 mL/kg body weight to a maximum of 360 mL; another product with equivalent caloric and nutrient content may be substituted for Boost) measured at 60 and 90 min after the start of consumption.
- 6. Involvement in intensive diabetes management defined as self monitoring of glucose values no less than a mean of three times each day averaged over each week and by the administration of three or more insulin injections each day or insulin pump therapy. Such management must be under the direction of an endocrinologist, diabetologist, or diabetes specialist with at least 3 clinical evaluations during the 12 months prior to study enrollment.
- 7. At least one episode of severe hypoglycemia defined as an event with one of the following symptoms: memory loss; confusion; uncontrollable behavior; irrational behavior; unusual difficulty in awakening; suspected seizure; seizure; loss of consciousness; or visual symptoms in which the subject was unable to treat him/herself and which was associated with either a blood glucose level <54 mg/dL [3.0 mmol/L] or prompt recovery after oral carbohydrate, IV glucose, or glucagon administration), in the 12 months prior to study enrollment.

- 8. Reduced awareness of hypoglycemia as defined by a Clarke score of 4 or more OR a HYPO score greater than or equal to the 90th percentile (1047) during the screening period and within the last 6 months prior to randomization;

#### OR

Marked glycemic lability characterized by wide swings in blood glucose despite optimal diabetes therapy and defined by an LI score greater than or equal to the 90th percentile (433 mmol/L/h·wk) during the screening period and within the last 6 months prior to randomization;

#### OR

A composite of a Clarke score of 4 or more and a HYPO score greater than or equal to the 75th percentile (423) and an LI greater than or equal to the 75th percentile (329) during the screening period and within the last 6 months prior to randomization.

#### 4.2 Exclusion Criteria

Patients who meet *any* of these criteria are *not* eligible for participation in the study:

- 1. Body mass index (BMI) >30 kg/m^2 or patient weight  $\le$ 50kg.
- 2. Insulin requirement of >1.0 IU/kg/day or <15 U/day.
- 3. HbA1c > 10%.
- 4. Untreated proliferative diabetic retinopathy.
- 5. Blood Pressure: SBP > 160 mmHg or DBP > 100 mmHg.
- 6. Measured glomerular filtration rate (using iohexol) of <80 mL/min/1.73 m^2 (or for subjects with an iodine allergy, calculated using the subject's measured serum creatinine and the Modification of Diet in Renal Disease [MDRD] study estimation formula). Strict vegetarians (vegans) with a calculated GFR <70 mL/min/1.73 m^2 are excluded. The absolute (raw) GFR value will be used for subjects with body surface areas >1.73 m^2.
- 7. Presence or history of macroalbuminuria (>300mg/g creatinine).
- 8. Presence or history of panel-reactive anti-HLA antibodies above background by flow cytometry.
- 9. For female subjects: Positive pregnancy test, presently breast-feeding, or unwillingness to use effective contraceptive measures for the duration of the study and 4 months after discontinuation. For male subjects: intent to procreate during the duration of the study or within 4 months after discontinuation or unwillingness to use effective measures of contraception. Oral contraceptives, Norplant®, Depo-Provera®, and barrier devices with spermicide are acceptable contraceptive methods; condoms used alone are not acceptable.
- 10. Active infection including hepatitis B, hepatitis C, HIV, or tuberculosis (TB) as determined by a positive skin test or clinical presentation, or under treatment for suspected TB. Positive tests are acceptable only if associated with a history of previous vaccination in the absence of any sign of active infection. Positive tests are otherwise not acceptable, even in the absence of any active infection at the time of evaluation.
- 11. Negative screen for Epstein Barr virus (EBV) by IgG determination.

- 12. Invasive aspergillus infection, histoplasmosis, and coccidioidomycosis infection within one year prior to study enrollment.
- 13. Any history of malignancy except for completely resected squamous or basal cell carcinoma of the skin.
- 14. Known active alcohol or substance abuse.
- 15. Baseline Hb below the lower limits of normal at the local laboratory; lymphopenia ( $<1,000/\mu L$ ), neutropenia ( $<1,500/\mu L$ ), or thrombocytopenia (platelets  $<100,000/\mu L$ ).
- 16. A history of Factor V deficiency.
- 17. Any coagulopathy or medical condition requiring long-term anticoagulant therapy (e.g., warfarin) after transplantation (low-dose aspirin treatment is allowed) or patients with an international normalized ratio (INR) >1.5.
- 18. Severe co-existing cardiac disease, characterized by *any one* of these conditions:
  - a) recent myocardial infarction (within past 6 months).
  - b) evidence of ischemia on functional cardiac exam within the last year.
  - c) left ventricular ejection fraction <30%.
- 19. Persistent elevation of liver function tests at the time of study entry. Persistent serum glutamic-oxaloacetic (SGOT [AST]), serum glutamate pyruvate transaminase (SGPT [ALT]), Alk Phos or total bilirubin, with values >1.5 times normal upper limits will exclude a patient.
- 20. Symptomatic cholecystolithiasis.
- 21. Acute or chronic pancreatitis.
- 22. Symptomatic peptic ulcer disease.
- 23. Severe unremitting diarrhea, vomiting or other gastrointestinal disorders potentially interfering with the ability to absorb oral medications.
- 24. Hyperlipidemia despite medical therapy (fasting low density lipoprotein [LDL]) cholesterol >130 mg/dL, treated or untreated; and/or fasting triglycerides >200 mg/dL).
- 25. Receiving treatment for a medical condition requiring chronic use of systemic steroids, except for the use of ≤5 mg prednisone daily, or an equivalent dose of hydrocortisone, for physiological replacement only.
- 26. Treatment with any anti-diabetic medication other than insulin within 4 weeks of enrollment.
- 27. Use of any investigational agents within 4 weeks of enrollment.

- 28. Administration of live attenuated vaccine(s) within 2 months of enrollment.
- 29. Any medical condition that, in the opinion of the investigator, will interfere with safe participation in the trial.
- 30. Treatment with any immunosuppressive regimen at the time of enrollment.
- 31. A previous islet transplant.
- 32. A previous pancreas transplant, unless the graft failed within the first week due to thrombosis, followed by pancreatectomy and the transplant occurred more than 6 months prior to enrollment.

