- 15. Baseline Hb below the lower limits of normal at the local laboratory; lymphopenia  $(<1,000/\mu L)$ , neutropenia  $(<1,500/\mu L)$ , or thrombocytopenia (platelets  $<100,000/\mu L)$ .
- 16. A history of Factor V deficiency.

- 17. Any coagulopathy or medical condition requiring long-term anticoagulant therapy (*e.g.*, warfarin) after transplantation (low-dose aspirin treatment is allowed) or patients with an international normalized ratio (INR) >1.5.
- 18. Severe co-existing cardiac disease, characterized by *any one* of these conditions:
  - a) recent myocardial infarction (within past 6 months).
  - b) evidence of ischemia on functional cardiac exam within the last year.
  - c) left ventricular ejection fraction <30%.
- 19. Persistent elevation of liver function tests at the time of study entry. Persistent serum glutamic-oxaloacetic transaminase (SGOT [AST]), serum glutamate pyruvate transaminase (SGPT [ALT]), Alk Phos or total bilirubin, with values >1.5 times normal upper limits will exclude a patient.
- 20. Symptomatic cholecystolithiasis.
- 21. Acute or chronic pancreatitis.
- 22. Symptomatic peptic ulcer disease.
- 23. Severe unremitting diarrhea, vomiting or other gastrointestinal disorders potentially interfering with the ability to absorb oral medications.
- 24. Hyperlipidemia despite medical therapy (fasting low-density lipoprotein [LDL] cholesterol >130 mg/dL, treated or untreated; and/or fasting triglycerides >200 mg/dL).
- 25. Receiving treatment for a medical condition requiring chronic use of systemic steroids, except for the use of ≤5 mg prednisone daily, or an equivalent dose of hydrocortisone, for physiological replacement only.
- 26. Treatment with any anti-diabetic medication other than insulin within 4 weeks of enrollment
- 27. Use of any investigational agents within 4 weeks of enrollment.
- 28. Administration of live attenuated vaccine(s) within 2 months of enrollment.
- 29. Any medical condition that, in the opinion of the investigator, will interfere with safe participation in the trial.
- 30. Treatment with any immunosuppressive regimen at the time of enrollment.
- 31. A previous islet transplant.

32. A previous pancreas transplant, unless the graft failed within the first week due to thrombosis, followed by pancreatectomy and the transplant occurred more than 6 months prior to enrollment.

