### 7.3 Baseline Visits

Once enrolled, subjects will return every 3months to assess the adequacy of their diabetes care, determine the HbA1c, and complete hypoglycemia and glycemic lability questionnaires in order to ensure continued eligibility for transplantation. Additional tests will be repeated as indicated in the timeline provided in the appendix.

Hypoglycemia will be assessed by completing 1) the Clarke survey of reduced hypoglycemia awareness, 2) the Ryan hypoglycemia score, and 3) the Hypoglycemia Fear Survey.

Glycemic lability will be assessed by calculating 1) the mean amplitude of glycemic excursions from 2 consecutive days of 7 blood glucose measurements each day, and 2) the Ryan lability index.

On one occasion (repeated annually as necessary), a hypoglycemic clamp will be performed to evaluate glucose counter-regulation after an overnight admission to the GCRC.

On one occasion (repeated annually as necessary), a continuous glucose monitoring system will be employed for 72-hours to assess the duration of hypo- and hyperglycemic episodes.

Insulin sensitivity will be assessed by a frequently-sampled intravenous glucose tolerance test (FSIGT) and euglycemic clamp. The euglycemic clamp will serve to validate the FSIGT-derived index of insulin sensitivity and provide normoglycemic control data for the hypoglycemic clamp. Both the FSIGT and a euglycemic clamp will be done annually, as will a hypoglycemic clamp. One clamp will be performed on the initial overnight GCRC admission. The remaining clamp will be done on the second overnight GCRC admission. The performance of the euglycemic clamp will occur in randomized order with the hypoglycemic clamp (above). Retinopathy will be evaluated by photography on an annual basis.

During this time of eligibility prior to transplant, additional baseline immunologic mechanistic assays will be performed as indicated in the timeline provided in the appendix. Their descriptions can be found in a subsequent section titled Mechanistic Assays.

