#### 7.4 Randomization

Once a compatible islet prep becomes available, subject eligibility will be re-confirmed. Eligible subjects will be randomized on Day -2 relative to transplant, between CIT-05 and CIT-07. Subjects randomized will receive immunosuppressive therapy beginning on Day -2 (see Section 5 for full description of Study Treatment Regimen). Subjects will receive the initial islet transplant on Day 0 and will continue the immunosuppression regimen detailed in Section 5.

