				P	RCH	IVED	SAMI	PLES								
Serum		Х								X			Х	X	Χ	Х
PBMC & Plasma		Х								Х			Х	Х	X	Χ
RNA		Х								Х			Х	Χ	Χ	Х

 WL = Waiting List. BL = Baseline. Repeat assessments as indicated (i.e. yrly, q3mo), while subject is on the waiting list. All one-time WL/BL assessments should be completed on Day -2 whenever possible, but always prior to start of immunosuppression. For repeat WL/BL assessments, results from test done closest to the start of immunosuppression will be used as the baseline value.

<sup>2 Day 0 = the day of transplant. This SOE applies to the  $1^{st}$ ,  $2^{nd}$ , and  $3^{rd}$  transplant as applicable. The SOE is restarted at Day 0 for each subsequent transplant.

<sup>3 Informed Consent #1 includes information on CIT-07 and CIT-05 protocols.

<sup>4 Informed Consent #2 includes information specific to CIT-05. IC #2 must be signed immediately after randomization.

<sup>5 FOBT (take-home multiple sample method) or FIT w/in last yr, flexible sigmoidoscopy w/in last 5 yrs, double-contrast barium enema w/in last 5 yrs, colonoscopy w/in last 10 yrs. All positive tests should be followed up with colonoscopy.

<sup>6Retinopathy eval includes fundoscopic pictures for WL/BL assessments and Y1. Screening retinopathy evaluation should be done per site-specific standards.

<sup>7 Chemistry includes: Sodium, albumin, magnesium, chloride, potassium, alk phosphatase, total bilirubin, CO2, creatinine, ALT (SGPT), BUN, gamma GT, glucose, AST (SGOT), calcium, phosphorus.

<sup>8 Complete pregnancy test within 72 hours prior to randomization.

<sup>9 Serology includes: HBc Ab, HBs Ab, HBs Ag, HCV Ab, HIV, and HTLV-I/II. Do not repeat Hepatitis B tests if HBs Ab was previously positive.

<sup>10 Repeat only if previous test was negative.

<sup>11 Repeat for subsequent transplant(s).

<sup>12 Sample used for crossmatch may be obtained up to 60 days prior to the start of immunosuppression, as long as there is no evidence of infections or transfusions since the time the sample was drawn. Repeat crossmatch for subsequent transplants.

<sup>13 C-peptide should be done locally and drawn fasting, and twice between 1-3 hours post-prandial on Day 3 and Day 7 post-transplant.

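### Exclusions 28 (live vaccine) and 12 (invasive fungal infection) count back from enrollment, so after a wait on the transplant list they need not cover the period just before lymphocyte-depleting induction on Day -2

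*Protocol*

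**What the plan says.** Section 4.2, repeated in the synopsis, ties several exclusions to enrollment. Exclusion 28 reads "Administration of live attenuated vaccine(s) within 2 months of enrollment". Exclusion 12 covers three invasive fungal infections in the year before enrollment. Exclusions 26, 27 and 30 read "Treatment with any anti-diabetic medication other than insulin within 4 weeks of enrollment", "Use of any investigational agents within 4 weeks of enrollment" and "Treatment with any immunosuppressive regimen at the time of enrollment".

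Enrollment is not the start of treatment. Under sections 7.1 and 7.2, eligible subjects are enrolled, given a number and put on the transplant waiting list. Section 7.3 continues: "Once enrolled, subjects will return every 3months to assess the adequacy of their diabetes care". Footnote 1 of Appendix 1 says: "Repeat assessments as indicated (i.e. yrly, q3mo), while subject is on the waiting list". Randomization comes later, under section 7.4: "Once a compatible islet prep becomes available, subject eligibility will be re-confirmed". Immunosuppression then begins on Day -2.

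Inclusion 8 in section 4.1 uses a different anchor. Its hypoglycemia and lability scores must be met "during the screening period and within the last 6 months prior to randomization".

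**The concern.** A look-back exclusion works only if the interval it inspects ends near the exposure it guards against. Here the exposure is combined T- and B-cell depletion starting on Day -2. Section 5.2.1.1 cites B-lymphocyte depletion of more than 6 months at this rituximab dose. If the interval ends at enrollment and the subject then waits, recent events fall outside it.

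The stake is subject safety at induction. No estimate, confidence interval or sample size in section 10 depends on the point.

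**Working it through.** The plan gives no figure to reproduce. The check compares dates.

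**Inputs**
- Window length L: 2 months for live vaccine (exclusion 28), 12 months for invasive fungal infection (exclusion 12), 4 weeks for investigational agents and non-insulin anti-diabetic drugs (exclusions 27 and 26). All from section 4.2.
- Start of exposure: Day -2, at randomization (section 7.4).
- Wait W from enrollment to Day -2: not stated, so it is an assumption. The yearly repeats in section 7.3 and Appendix 1 show that the plan allows for waits of about a year, but they do not give a length.

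**Question.** Of the L months ending on Day -2, how many does the written window cover?

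*One-sided reading (before enrollment only).* Cover = max(0, L − W).

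*Two-sided reading (before or after enrollment).* The window runs from L before to L after enrollment, so cover = min(L, max(0, 2L − W)). The wording of exclusions 26 to 28 permits this reading. Exclusion 12 refers only to the time before enrollment, so it is one-sided.

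| Criterion | Wait W | One-sided cover | Two-sided cover |
|---|---|---|---|
| 28, L = 2 months | 0 | 2 − 0 = 2 months | 2 months |
| 28 | 1 month | 2 − 1 = 1 month | 2 months |
| 28 | 2 months | 0 | 2 months |
| 28 | 3 months | 0 | 4 − 3 = 1 month |
| 28 | 4 months or more | 0 | 0 |
| 12, L = 12 months | 6 months | 12 − 6 = 6 months | not applicable |
| 12 | 12 months or more | 0 | not applicable |
| 26 and 27, L = 4 weeks | 2 weeks | 4 − 2 = 2 weeks | 4 weeks |
| 26 and 27 | 4 weeks | 0 | 4 weeks |
| 26 and 27 | 8 weeks or more | 0 | 0 |

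**Example.** A subject waits 12 months and receives a live vaccine one week before Day -2. The vaccination falls more than 11 months after enrollment, outside a 2-month window on either reading. Exclusion 28 is not met.

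**Do the later checks catch it?**
- Section 7.4 requires re-confirmation. Applying exclusion 28 again on Day -2 still measures from enrollment.
- Appendix 1 marks the inclusion/exclusion evaluation at the waiting-list/baseline column. Footnote 1 asks for one-time assessments in that column on Day -2 where possible. This repeats the check without restating its reference date.
- The 3-monthly visits in section 7.3 name diabetes care, HbA1c and questionnaires. The admission check in section 7.5 rests on blood work, urinalysis, EKG and chest X-ray. Neither names a vaccine or infection history.
- Section 5.5 does not list live vaccines.

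**Is another anchor already in use?** Yes. Besides inclusion 8, the pregnancy test is timed within 72 hours before randomization, and the crossmatch sample may be at most 60 days old at the start of immunosuppression (Appendix 1, footnotes 8 and 12).

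**The case against.** The strongest defense is that the plan clearly intends a live eligibility check at transplant. It has 3-monthly visits to ensure continued eligibility, re-confirmation in section 7.4 and an evaluation timed to Day -2 where possible. A sensible site would apply the windows to Day -2, since otherwise the re-check achieves nothing for these items. That is a fair account of the intent. It does not cure the text, because no passage tells the site to measure from Day -2 and two sites could answer differently.

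The defense succeeds on several wider readings that a reader might infer.
- *That exclusions 26, 27 and 30 leave subjects equally exposed.* Section 5.5 prohibits other investigational products, immunosuppressants and anti-diabetic agents, and wait-listed subjects are already enrolled. If it applies during the wait, most of that gap closes. It sits in the treatment chapter and does not say so.
- *That infection screening in general lapses.* Exclusion 10 on active infection has no enrollment anchor, and PPD and serology are repeated yearly on the list. Exclusion 29 has no date limit either. For exclusion 12, what remains is mainly an invasive fungal infection acquired during the wait and no longer active by Day -2.
- *That inclusion 7 (severe hypoglycemia in the 12 months before enrollment) fails in the same way.* It is an entry-history criterion. Current severity is governed by inclusion 8, which is tied to randomization, and hypoglycemic events are recorded from enrollment consent onward.
- *That the whole 24-month accrual period can be taken as one subject's wait, or that CIT-07 needs the same change.* No wait length is stated, and the CIT-07 criteria are not in the documents.

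**Conclusion.** The point holds for exclusions 28 and 12. As worded, they are measured from a date that can be well before induction, and the scheduled re-checks do not move that date. The live-vaccine criterion is the clearer case, because no other provision names live vaccines. Its cover of the 2 months before Day -2 is gone from a 2-month wait on the one-sided reading and from a 4-month wait on the two-sided reading. For exclusion 12, cover is gone from a 12-month wait.

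For exclusions 26, 27 and 30 the defect is smaller: the plan does not say whether section 5.5 applies from enrollment.

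The conclusion rests on reading enrollment as the step in section 7.1 that precedes the waiting list. Sections 7.2, 7.3 and 8.2.1 support this, although section 10.5 uses the word more loosely. How many subjects would be affected cannot be computed, because waiting times are not given. The planned analyses are unchanged.

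**What to change.** Reconcile section 4.2 and the synopsis with sections 7.4 and 7.5 and Appendix 1, so that the reference date is explicit. Leave all window lengths as they are. State that the Day -2 re-confirmation applies exclusions 12 and 28 relative to randomization, the anchor inclusion 8 already uses. For exclusions 26, 27 and 30, either do the same or state in section 5.5 that its prohibitions apply from enrollment. Add the matching history questions to the admission check in section 7.5.

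The cost is amendment wording and a short history check on Day -2. Occasionally a wait-listed subject would be passed over for one islet preparation.
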